#### **4.5 Participant Replacement Strategy**

Subjects who fail to complete study therapy will not be replaced.

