#### **6.1.4.6 Follow-up Visits**

Follow-up after Cycle 2 (Cycle 6 for part B) will be conducted per Standard of Care. Patients will be tracked for subsequent therapy, response, progression-free, and overall survival up to 5 years.

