**Part B:**

Based on the rationale outlined in the background section, we plan to enroll 20 additional patients in part B (for a total of 50 between part A and B). We will only accrue advanced stage patients (stage 3 or 4) for this portion of the study.

In part A, we have enrolled 29 patients, of whom 18 were stage 3 or 4. We expect the final patient in part A will be advanced stage, and therefore we expect to have 19 total advanced stage patients in Part A. When combined with expected accrual of 20 patients in Part B, we expect to have 39 total advanced stage patients that are evaluable for efficacy data.

Given our concerns with PET-based assessments, we will analyze the 39 advanced patients for efficacy by estimating 1-year EFS. An event will be defined as progression, biopsy proven recurrence, initiation of next line of chemotherapy, or death. The benchmark to deem this regimen as potentially efficacious will be 1-year EFS of 85% for this population (intermediate between the more commonly used ABVD and the more toxic but less commonly used brentuximab vedotin + AVD). Towards this end, we shall consider an observed 1-year EFS among the 39 patients of at least 0.85 (33 or more of 39) to be potentially efficacious and warrant further study of the current regimen (note that this will not necessarily imply a statistically significant improvement on this benchmark). The decision will also take into consideration secondary endpoints. The table below summarizes the probability of observing a 1-year EFS of at least 85% under a variety of assumed-true 1-year EFS values.

Assumed-true 1-year EFS	Probability of observed 1-year EFS of at least 85%
75%	0.11
80%	0.31
85%	0.63
90%	0.91

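### The Part B go rule is a count of 33 out of 39, and the plan does not say how a patient with unknown 12-month status is counted

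*Combined protocol and SAP*

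**What the plan says.** SAP section 7.1, Part B, pools the expected 19 advanced-stage patients from Part A with 20 from Part B: "we expect to have 39 total advanced stage patients that are evaluable for efficacy data". On the analysis it says that "we will analyze the 39 advanced patients for efficacy by estimating 1-year EFS". On events: "An event will be defined as progression, biopsy proven recurrence, initiation of next line of chemotherapy, or death". Loss to follow-up is not among them.

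The benchmark is an 85% 1-year EFS, and the go criterion is "an observed 1-year EFS among the 39 patients of at least 0.85 (33 or more of 39". A table headed "Probability of observed 1-year EFS of at least 85"% gives 0.11, 0.31, 0.63 and 0.91 for true values of 75%, 80%, 85% and 90%. The SAP adds that meeting the criterion need not mean a statistically significant improvement, and that secondary endpoints will also be weighed.

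On follow-up, section 6.1.4.6 says: "Follow-up after Cycle 2 (Cycle 6 for part B) will be conducted per Standard of Care". It then says that patients are tracked for outcomes for up to 5 years. Section 4.5 says: "Subjects who fail to complete study therapy will not be replaced". Section 4.4 lists loss to follow-up only as a reason to discontinue study treatment.

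**The concern.** One-year EFS is a time-to-event quantity, but the criterion is written as a number of patients out of a fixed 39. A patient who drops out of contact at month 8 without an event has not been shown to be event-free at 12 months, and has not had an event either. The plan does not say whether that patient counts towards the 33, counts against it, leaves the denominator, or is censored.

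Such patients are plausible here. By the dosing grid, cycle 6 day 15 falls on study day 5 × 28 + 15 = 155. The last scheduled PET/CT for six-cycle patients, 28 to 35 days after the expected last chemotherapy, then falls on about day 183 to 190. No disease assessment is mandated between then and 12 months.

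This is the only numerical efficacy criterion in an open-label, single-arm trial. If the choice is left open, it can be made after the outcomes are known.

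**Working it through.** **Inputs.** From SAP 7.1, Part B: n = 39, go count 33, benchmark 0.85, and the four printed probabilities. The number lost, m, is an assumption, because the documents give no rate. I use 1 to 3 of 39 (3% to 8%).

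**Step 1: reproduce the plan's table.** With X ~ Binomial(39, p), P(X ≥ 33) is 0.111, 0.312, 0.633 and 0.911 at p = 0.75, 0.80, 0.85 and 0.90. All four match. The table therefore assumes complete 12-month data.

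**Step 2: check the two forms of the cut-off.** 33/39 = 0.846, which is below 0.85, and 34/39 = 0.872. The smallest count that truly reaches 0.85 is 34, and P(X ≥ 34) is 0.05, 0.18, 0.46 and 0.81. The proportion and the count in the criterion therefore disagree even with nobody lost.

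**Step 3: m patients lost before any event.** The other 39 − m have known status, so X ~ Binomial(39 − m, p).
- Lost patients cannot be among the 33: P(go) = P(X ≥ 33).
- Lost patients count as event-free: P(go) = P(X ≥ 33 − m).

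| m | Lost patients | 75% | 80% | 85% | 90% |
|---|---|---|---|---|---|
| 0 | none | 0.111 | 0.312 | 0.633 | 0.911 |
| 1 | not event-free | 0.060 | 0.200 | 0.485 | 0.825 |
| 2 | not event-free | 0.028 | 0.112 | 0.330 | 0.691 |
| 3 | not event-free | 0.011 | 0.052 | 0.191 | 0.509 |
| 1 | event-free | 0.128 | 0.340 | 0.659 | 0.920 |
| 2 | event-free | 0.147 | 0.370 | 0.685 | 0.929 |
| 3 | event-free | 0.168 | 0.401 | 0.710 | 0.937 |

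Two intermediate conventions with m = 3:
- Excluding the lost patients and requiring at least 0.85 of the remaining 36 (31 of 36) gives 0.083, 0.246, 0.541 and 0.855.
- Kaplan-Meier with cut 33/39 and losses spread evenly over the year gives about 0.07, 0.22, 0.50 and 0.84 (20,000 simulated trials, exponential event times).

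**Step 4: Kaplan-Meier and the choice of cut-off.** I simulated exponential event times and about 5% lost by 12 months. At true 85%, P(go) is about 0.62 with cut 0.84, 0.52 with cut 33/39 and 0.48 to 0.49 with cut 0.85. At true 90% it is about 0.90 with cut 0.84 and 0.84 to 0.85 with cut 33/39.

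Much of the drop at 33/39 is a tie effect. With one patient lost at the start and six events among the other 38, the estimate is 32/38 = 0.842. That is just under 0.846 but above 0.84. With no losses, a cut of 0.84 admits 33/39 (0.846) and rejects 32/39 (0.821), so it keeps the plan's intended count.

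**The case against.** A reader might infer that a few losses push the decision far from the printed probabilities whatever convention is used. The documents do not support that. The falls to 0.19 (true 85%) and 0.51 (true 90%) need three losses and a reading in which lost patients cannot be among the 33. The plan never adopts that reading, and loss is not one of its events. If lost patients count as event-free, P(go) rises modestly. With exclusion or Kaplan-Meier and three lost, it falls by about 0.06 to 0.13 at true 85% to 90%.

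Nor do the documents rule out Kaplan-Meier. The SAP speaks of estimating 1-year EFS and puts the count in brackets after a proportion, for 39 patients it expects to be evaluable. It leaves the estimator unstated.

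It is also tempting to treat non-replacement in section 4.5 as a source of missing outcomes. That section concerns patients who fail to complete therapy, and section 4.4 provides for continued monitoring of patients who discontinue treatment. Tracking for up to 5 years means that 12-month status can be obtained for anyone who stays in contact.

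Finally, the count does not decide alone. This is a pilot with no formal test, and secondary endpoints are weighed too.

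All of this limits the size of the problem but does not remove it. The printed table is a complete-data count, no text covers unknown status, and the secondary endpoints carry no thresholds or weights that would settle the matter.

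**Conclusion.** The point holds as a gap in the definition of the Part B primary endpoint and its go rule. The printed probabilities are arithmetically right for 33 of 39, but they apply only if 12-month status is known for every patient.

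Under the assumption of 1 to 3 losses, P(go) at true 85% (printed 0.63) runs from 0.49 down to 0.19 if lost patients are not counted event-free, and from 0.66 up to 0.71 if they are. At true 90% (printed 0.91) the ranges are 0.83 down to 0.51 and 0.92 up to 0.94. These figures rest on an assumed number of losses, on loss before any event, and on independence of loss and outcome. If 12-month status is obtained for all 39, the gap has no effect on the result. The mismatch between 0.85 and 33/39 would remain.

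**What to change.** In SAP 7.1, Part B:

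1. State that 1-year EFS is the Kaplan-Meier estimate at 12 months from a named time origin (for example, first dose), with patients without an event censored at their last disease assessment. Report it with a 95% confidence interval (log-log). Keep the raw count as description only.
2. Give one numerical cut-off. Either set it at 0.84, which keeps 33 of 39 when nobody is lost, or keep 0.85, which needs 34 of 39 and gives 0.05, 0.18, 0.46 and 0.81 with no losses.
3. Recalculate the table for the chosen estimator and cut-off, with a stated loss assumption.
4. Add a sensitivity analysis that counts patients of unknown 12-month status first as failures and then as event-free.

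The cost is a few sentences and one table, with no added patients or visits. The go probability will be somewhat below the printed one when patients are lost. With about 5% lost and true EFS 85%, it is about 0.62 at cut 0.84, 0.52 at cut 33/39 and 0.48 to 0.49 at cut 0.85, against the printed 0.63. The change should be made before the Part B outcomes are analysed.

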## 8.0 LABELING, PACKAGING, STORAGE AND RETURN OF CLINICAL SUPPLIES

### 8.1 Investigational Product

The investigator shall take responsibility for and shall take all steps to maintain appropriate records and ensure appropriate supply, storage, handling, distribution and usage of investigational product in accordance with the protocol and any applicable laws and regulations.

Pembrolizumab will be provided by Merck as summarized in Table 8.

Table 8 Product Descriptions

Product Name & Potency	Dosage Form
Pembrolizumab 100 mg/ 4mL	Solution for Injection

### 8.2 Packaging and Labeling Information

Supplies will be labeled in accordance with regulatory requirements.

### 8.3 Clinical Supplies Disclosure

This trial is open-label; therefore, the participant, the trial site personnel, the Sponsor and/or designee are not blinded to treatment. Drug identity (name, strength) is included in the label text; random code/disclosure envelopes or lists are not provided.

### 8.4 Storage and Handling Requirements

Clinical supplies must be stored in a secure, limited-access location under the storage conditions specified on the label.

Receipt and dispensing of trial medication must be recorded by an authorized person at the trial site.

Clinical supplies may not be used for any purpose other than that stated in the protocol.

### 8.5 Returns and Reconciliation

The investigator is responsible for keeping accurate records of the clinical supplies received from Merck or designee, the amount dispensed to and returned by the participants and the amount remaining at the conclusion of the trial.

Upon completion or termination of the study, all unused and/or partially used investigational product will be destroyed at the site per institutional policy. It is the Investigator's responsibility to arrange for disposal of all empty containers, provided that procedures for proper disposal have been established according to applicable federal, state, local and institutional guidelines and procedures, and provided that appropriate records of disposal are kept.

## **9.0 DATA AND SAFETY MONITORING PLAN**

Ongoing trial oversight is carried out by the Principal Investigator and study staff. These individuals will communicate on a regular basis to review recently acquired data and adverse events. The data recorded within the research charts and protocol database is compared with the actual data that is available from the medical record and/or clinical histories. Data detailed in the research case report forms includes the nature and severity of all toxicities, which are also reported as described above.

Institutional support of trial monitoring will be in accordance with the FHCRC/UW Cancer Consortium Institutional Data and Safety Monitoring Plan. Under the provisions of this plan, FHCRC Clinical Research Support coordinates monitoring for data accuracy and compliance by consultants, contract research organizations, or FHCRC employees unaffiliated with the conduct of the study. Independent monitoring visits occur at specified intervals determined by the assessed risk level of the study and the findings of previous visits per the institutional DSMP.

In addition, protocols are reviewed at least annually and as needed by the Consortium Data Safety Monitoring Committee (DSMC), FHCRC Scientific Review Committee (SRC) and the FHCRC/Cancer Consortium Institutional Review Board (IRB). The review committees evaluate accrual, adverse events, stopping rules, and adherence to the applicable data and safety monitoring plan for studies actively enrolling or treating patients. The IRB reviews the study progress and safety information to assess continued acceptability of the risk-benefit ratio for human subjects. Approval of committees as applicable is necessary to continue the study.

The trial will comply with the standard guidelines set forth by these regulatory committees and other institutional, state and federal guidelines.

The IRB has the authority to suspend or terminate the study should it be deemed necessary.

### **9.1 RECORDS**

Research staff under the supervision of the investigators will maintain case report forms and secured databases on the relevant clinical and laboratory data. Records maintained in investigators' offices will be secured with access limited to study personnel. Authorization for access to medical records will be obtained from all patients in accordance with provisions of the Health Insurance Portability and Accountability Act (HIPAA).

## 9.2 REGULATORY RESPONSIBILITIES OF SPONSOR-INVESTIGATOR

The Sponsor-Investigator will ensure that the study is conducted in accordance with all applicable institutional, state, and federal regulatory requirements, including, but not limited to: compliance with requirements for IRB and other regulatory approvals, monitoring responsibilities, reporting obligations, and compliance with standards for written informed consent from all patients entering the study. In addition, the sponsor will ensure oversight of the study via data and safety monitoring as described above.

## 11.0 APPENDICES

### Appendix 1: ECOG Performance Status

Grade	Description
0	Normal activity. Fully active, able to carry on all pre-disease performance without restriction.
1	Symptoms, but ambulatory. Restricted in physically strenuous activity, but ambulatory and able to carry out work of a light or sedentary nature (e.g., light housework, office work).
2	In bed <50% of the time. Ambulatory and capable of all self-care, but unable to carry out any work activities. Up and about more than 50% of waking hours.
3	In bed >50% of the time. Capable of only limited self-care, confined to bed or chair more than 50% of waking hours.
4	100% bedridden. Completely disabled. Cannot carry on any self-care. Totally confined to bed or chair.
5	Dead.

\* As published in Am. J. Clin. Oncol.: *Oken, M.M., Creech, R.H., Tormey, D.C., Horton, J., Davis, T.E., McFadden, E.T., Carbone, P.P.: Toxicity And Response Criteria Of The Eastern Cooperative Oncology Group. Am J Clin Oncol 5:649-655, 1982.* The Eastern Cooperative Oncology Group, Robert Comis M.D., Group Chair.

## **Appendix 2: Common Terminology Criteria for Adverse Events V4.0 (CTCAE)**

The descriptions and grading scales found in the revised NCI Common Terminology Criteria for Adverse Events (CTCAE) version 4.0 will be utilized for adverse event reporting.

**Appendix 3: Response Criteria: “The Lugano Classification”**

Response and Site	PET-CT-Based Response	CT-Based Response
Complete	Complete metabolic response	Complete radiologic response (all of the following)
Lymph nodes and extralymphatic sites	Score 1, 2, or 3* with or without a residual mass on 5PS †  It is recognized that in Waldeyer's ring or extranodal sites with high physiologic uptake or with activation within spleen or marrow (eg, with chemotherapy or myeloid colony-stimulating factors), uptake may be greater than normal mediastinum and/or liver. In this circumstance, complete metabolic response may be inferred if uptake at sites of initial involvement is no greater than surrounding normal tissue even if the tissue has high physiologic uptake	Target nodes/nodal masses must regress to $\leq 1.5$ cm in LD $i$
Nonmeasured lesion	Not applicable	No extralymphatic sites of disease
Organ enlargement	Not applicable	Rgress to normal
New lesions	None	None
Bone marrow	No evidence of FDG-avid disease in marrow	Normal by morphology; if indeterminate, IHC negative
Partial	Partial metabolic response	Partial remission (all of the following)
Lymph nodes and extralymphatic sites	Score 4 or 5 † with reduced uptake compared with baseline and residual mass(es) of any size	$\geq 50\%$ decrease in SPD of up to 6 target measurable nodes and extranodal sites

Response and Site	PET-CT-Based Response	CT-Based Response
	At interim, these findings suggest responding disease	When a lesion is too small to measure on CT, assign 5 mm × 5 mm as the default value
	At end of treatment, these findings indicate residual disease	When no longer visible, 0 × 0 mm
		For a node > 5 mm × 5 mm, but smaller than normal, use actual measurement for calculation
Nonmeasured lesions	Not applicable	Absent/normal, regressed, but no increase
Organ enlargement	Not applicable	Spleen must have regressed by > 50% in length beyond normal
New lesions	None	None
Bone marrow	Residual uptake higher than uptake in normal marrow but reduced compared with baseline (diffuse uptake compatible with reactive changes from chemotherapy allowed). If there are persistent focal changes in the marrow in the context of a nodal response, consideration should be given to further evaluation with MRI or biopsy or an interval scan	Not applicable
No response or stable disease	No metabolic response	Stable disease
Target nodes/nodal masses, extranodal lesions	Score 4 or 5 with no significant change in FDG uptake from baseline at interim or end of treatment	< 50% decrease from baseline in SPD of up to 6 dominant, measurable nodes and extranodal sites; no criteria for progressive disease are met

Response and Site	PET-CT-Based Response	CT-Based Response
Nonmeasured lesions	Not applicable	No increase consistent with progression
Organ enlargement	Not applicable	No increase consistent with progression
New lesions	None	None
Bone marrow	No change from baseline	Not applicable
Progressive disease	Progressive metabolic disease	Progressive disease requires at least 1 of the following
Individual target nodes/nodal masses	Score 4 or 5 with an increase in intensity of uptake from baseline and/or	PPD progression:  An individual node/lesion must be abnormal with: LDi > 1.5 cm and Increase by $\geq 50\%$ from PPD nadir and An increase in LDi or SDi from nadir 0.5 cm for lesions $\leq 2$ cm 1.0 cm for lesions $> 2$ cm In the setting of splenomegaly, the splenic length must increase by $> 50\%$ of the extent of its prior increase beyond baseline (eg, a 15-cm spleen must increase to $> 16$ cm). If no prior splenomegaly, must increase by at least 2 cm from baseline New or recurrent splenomegaly
Extranodal lesions	New FDG-avid foci consistent with lymphoma at interim or end-of-treatment assessment	

Response and Site	PET-CT-Based Response	CT-Based Response
Nonmeasured lesions	None	New or clear progression of preexisting nonmeasured lesions
New lesions	New FDG-avid foci consistent with lymphoma rather than another etiology (eg, infection, inflammation). If uncertain regarding etiology of new lesions, biopsy or interval scan may be considered	Regrowth of previously resolved lesions A new node > 1.5 cm in any axis A new extranodal site > 1.0 cm in any axis; if < 1.0 cm in any axis, its presence must be unequivocal and must be attributable to lymphoma Assessable disease of any size unequivocally attributable to lymphoma
Bone marrow	New or recurrent FDG-avid foci	New or recurrent involvement

- Abbreviations: 5PS, 5-point scale; CT, computed tomography; FDG, fluorodeoxyglucose; IHC, immunohistochemistry; LDi, longest transverse diameter of a lesion; MRI, magnetic resonance imaging; PET, positron emission tomography; PPD, cross product of the LDi and perpendicular diameter; SDi, shortest axis perpendicular to the LDi; SPD, sum of the product of the perpendicular diameters for multiple lesions.
- 4\* A score of 3 in many patients indicates a good prognosis with standard treatment, especially if at the time of an interim scan. However, in trials involving PET where escalation is investigated, it may be preferable to consider a score of 3 as inadequate response (to avoid undertreatment). Measured dominant lesions: Up to six of the largest dominant nodes, nodal masses, and extranodal lesions selected to be clearly measurable in two diameters. Nodes should preferably be from disparate regions of the body and should include, where applicable, mediastinal and retroperitoneal areas. Non-nodal lesions include those in solid organs (eg, liver, spleen, kidneys, lungs), GI involvement, cutaneous lesions, or those noted on palpation. Nonmeasured lesions: Any disease not selected as measured, dominant disease and truly assessable disease should be considered not measured. These sites include any nodes, nodal masses, and extranodal sites not selected as dominant or measurable or that do not meet the requirements for measurability but are still considered abnormal, as well as truly assessable disease, which is any site of suspected disease that would be difficult to follow quantitatively with measurement, including pleural effusions, ascites, bone lesions, leptomeningeal disease, abdominal masses, and other lesions that cannot be confirmed and followed by imaging. In Waldeyer's ring or in extranodal sites (eg, GI tract, liver, bone marrow), FDG uptake may be greater than in the mediastinum

with complete metabolic response, but should be no higher than surrounding normal physiologic uptake (eg, with marrow activation as a result of chemotherapy or myeloid growth factors).

- $\underline{\text{d}}\text{†}$  PET 5PS: 1, no uptake above background; 2, uptake  $\leq$  mediastinum; 3, uptake  $>$  mediastinum but  $\leq$  liver; 4, uptake moderately  $>$  liver; 5, uptake markedly higher than liver and/or new lesions; X, new areas of uptake unlikely to be related to lymphoma.

## Appendix 4: Contraceptive Guidance and Pregnancy Testing

### Woman of Childbearing Potential (WOCBP)

A woman is considered fertile following menarche and until becoming post-menopausal unless permanently sterile (see below)

Women in the following categories are not considered WOCBP:

- Premenarchal
- Premenopausal female with 1 of the following:
  - Documented hysterectomy
  - Documented bilateral salpingectomy
  - Documented bilateral oophorectomy

Note: Documentation can come from the site personnel's review of the participant's medical records, medical examination, or medical history interview.

- Postmenopausal female
  - A postmenopausal state is defined as no menses for 12 months without an alternative medical cause.
    - A high follicle stimulating hormone (FSH) level in the postmenopausal range may be used to confirm a postmenopausal state in women not using hormonal contraception or hormonal replacement therapy (HRT). However, in the absence of 12 months of amenorrhea, confirmation with two FSH measurements in the postmenopausal range is required.
  - Females on HRT and whose menopausal status is in doubt will be required to use one of the non-hormonal highly effective contraception methods if they wish to continue their HRT during the study. Otherwise, they must discontinue HRT to allow confirmation of postmenopausal status before study enrollment.

